We will use KWP data to measure household purchasing of drinks in each of the four categories described above, as well as confectionery and toiletries. This is a commercial, continuously refreshed, representative panel of UK households (n=30,000) who record all food and beverage purchases brought into the home using a barcode scanner. Using quota sampling, the KWP panel is nationally representative in terms of region, occupational social class, age of main shopper and number of children in households. Most households stay in the panel for 2-3 years. Barcode

scanners capture detailed information on purchases (e.g. product line, package size, and price). This is linked to basic nutritional information, including sugar content. A validation study confirmed that KWP data closely reflected data from the Living Costs and Foods Survey (LCFS; described below), which is a similar government funded household panel.⁴⁴ However KWP may still include some underreporting of total energy consumption.⁴⁵

Until recently, a major limitation of KWP (and source of underreporting) was the exclusion of purchases that did not come into the home. Around one-third of UK soft drink purchases are for immediate consumption (and hence unlikely to come into the home).⁴⁶ To address this, since 2015, a representative sub-sample (n=8,000) of the KWP panel has recorded on-the-go purchases using a mobile phone app. We will include this to test the robustness of findings from the main panel.

We will study effects on purchasing of drinks in all four categories described above and confectionery in order to capture possible substitution effects across drinks, and to one other high sugar category (i.e. confectionery). Identifying decreases in purchases of levy-eligible drinks alongside increases in purchases of other drinks will increase our confidence that the effect on levy-eligible drinks is 'true'. Identifying decreases in purchases of levy-eligible drinks alongside increases in confectionery would alert us to possible unintended consequences of the intervention. Sales of toiletries are included as an unrelated category in order to act as a 'non-equivalent' control³⁸ which should be unaffected by the intervention, but which would be sensitive to wider changes in the grocery market or economy that might impact purchases of all items.

Outcome measures

Outcome measures will be:

- mean 4-weekly purchases of drinks (in litres and £) in each of four drinks categories per household

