- mean 4-weekly purchases of confectionery (in kg & £) per household
- mean 4-weekly total sugars (in kg and £) in drinks purchased in each of four categories per household
- mean 4-weekly total sugars (in kg and £) in confectionery purchased per household
- mean 4-weekly purchases of toiletries (in £) – the 'control' condition

We will use product-specific nutritional information within the KWP dataset to determine into which of our four categories drinks fall and to determine total sugar in drinks and confectionery.

Study period and sample size

We will include data from the main household panel from April 2014–March 2020. That is: two full years before intervention announcement to two full years after intervention implementation. Data from the on-the-go panel is only available from September 2015. We will include data from the on-the-go panel from September 2015-March 2020. That is: 7 months before intervention announcement to two full years after intervention implementation.

KWP data is provided aggregated into 4-weekly periods. KWP is unwilling to make more granular data available to us. This will provide 78 time points from the household panel, with 30,000 households per time point; and 60 time points from the on-the-go panel, with 8000 individuals per time point. This dataset therefore substantially exceeds current recommendations for minimum samples sizes for ITS analyses.

Data analysis

We will conduct controlled, multiple time points, ITS analyses for each outcome overall and then (where appropriate), separately for each drinks category. In all cases, purchases of toiletries will be used as a non-equivalent comparator.³⁸ The unit of analysis will be 4-weekly periods. We will include two ‘intervention’ points in each model – intervention announcement and intervention implementation. We will first conduct analyses in the whole sample. We will then disaggregate households by occupational social class of the head of household (assigned using the National Readership Survey (ABC1C2DE) categorisation), age group (in 10 year bands) of the main shopper, household composition and size. Interaction terms will be used to determine whether effects differ between groups. We will plot significant interactions to explore and interpret them.

Study 1c: the impact of the SDIL on consumption of drinks, confectionery and added sugar; overall and by age, sex and SEP

Study design

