Using the National Diet and Nutrition Survey (NDNS), we will use standard regression methods to study whether the announcement or implementation of the SDIL was associated with changes in consumption of drinks in four categories, confectionery and added sugars as a whole. We will study effects overall and whether effects differ by individual age, gender and SEP.

Data source

We will use NDNS data to measure consumption of drinks (in the four categories described above) and confectionery. This data is free to access for researchers from the UK Data Service. NDNS is an annual (since 2008), cross-sectional survey of people living in UK private households.⁴⁷ Participants complete a socio-demographic questionnaire and are given a prospective, estimated, 4-day food diary to complete. Diaries are reviewed at a follow-up interview. Parents or carers provide information for children <12 years. Food diaries collect information at the product level and are linked to a nutrient database. To date, 56% of individuals recruited have returned usable food diaries (3 or 4 completed days).⁴⁷ Weighting variables take account of selective non-response. Food diaries are one of the most accurate methods of capturing diet.⁴⁸ However, under-reporting of energy intake and selective under-reporting of less healthy foods (relative to purchase data) occurs.⁴⁴

We include consumption of drinks in each category as a direct measure of exposure to levy-eligible, and other, drinks. We are not aware of other pragmatic evaluations of soda taxes that have measured consumption of eligible drinks. As purchases may not entirely represent consumption (e.g. due to waste), this is an important evidence gap.

Nutritional composition of products consumed is included in NDNS. However, updating of this information can be *ad hoc*. Given we expect reformulation of many drinks during the evaluation, we will link contemporaneous total sugar content data on drinks from KWP to NDNS data. In the great majority of cases, all sugar in drinks (with the exception of fruit juices) is added sugar.

Outcome measures

Outcome measures, at the individual level, will be:

- mean daily consumption (ml) in each of the four categories of drinks
- mean daily consumption (g) of confectionery
- mean daily added sugars (g) consumed in drinks in each of the four categories

- mean daily added sugars (g) consumed in confectionery and from all sources

Study period

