7.2 WP2 – Impacts on medium to long term health outcomes

Study design

To estimate the impacts of the SDIL over longer time horizons, we will simulate a range of outcomes using a proportional multistate life table approach, adapting an existing life table model (PRIMEtime).⁵⁹ The results from WP1 will be used to estimate effect sizes in terms of sugary drink consumption and free sugars from drinks. The PRIMEtime model will then estimate the impact of these changes on health outcomes over the medium term (next 10 years), and long term (>10 years).

Proposed methods

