The health model will use a proportional multi-state life table approach.⁶⁰ It will be parameterised with data on disease incidence and mortality in the UK taken from the Office for National Statistics, linked datasets of HES and death certificates and disease registries. The diseases in the health model will include dental caries, T2DM, cardiovascular diseases, kidney disease and obesity-related cancers (i.e. cancers of the colon, kidney, liver, breast and pancreas). The results of WP1 will determine the change in mean soft drink consumption (ml/day) and the mean sugar concentration of soft drinks (g/ml). Using a method that we have previously developed to estimate the potential impact of the SDIL under different implementation scenarios⁵⁵, we will convert these outputs into measures of ‘equivalised sugar drink intake’. These changes will be translated into changes in body weight using bespoke meta-analyses of the effect of sugar drink consumption on body weight in both adults and children. For an overview of the trial literature on sugar drink consumption and body weight, see Schillinger et al. (2016).⁶¹ Changes in body weight will be translated into the health outcomes by estimating population impact fractions (PIFs), similar to methods used by the Global Burden of Disease project⁶². The PIFs will be based on hazard ratios linking body weight and the health outcomes, which will be drawn from meta-analyses of prospective cohort studies (e.g. Prospective Studies Collaboration, 2009; WCRF/AICR, 2007). For T2DM, we will model the health impact between soft drinks and disease outcome directly using results from prospective cohort studies.^{59 63} For dental caries we will model the impact between sugar consumption and disease outcome using results from a prospective cohort study.⁶⁴ Work has recently been completed to apply disease utility weights to the PRIMEtime model using a comparable study of population-based EQ-5D scores for the US population adapted for the UK by using UK-based time trade-off tariffs.⁶⁵

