For this project, we will further develop the PRIMEtime model in five ways. First, we will build the first part of the model that estimates changes in soft drink risk as a result of the SDIL, based on results drawn from elsewhere in this project. Here, the inputs will be changes in consumption of sugar drinks (from the interrupted time series analysis of the Kantar World Panel dataset) and changes in average sugar levels in sugar drinks (from the interrupted time series analysis of the foodDB dataset), which will provide population-level estimates that can be converted into changes in ‘equivalised sugar drink consumption’.

Second, we will adapt the existing model to incorporate dental caries, using the datasets described above. Third, we will extend the PRIMEtime model to incorporate children and adolescents who are high consumers of soft drinks by using age and sex-specific estimates of soft drink consumption derived from the NDNS. This will require us to make assumptions regarding how overweight and obesity tracks from childhood into adulthood, which will be informed by the literature. We will conduct sensitivity analyses to test how sensitive our results are to these

changes. However, with the exception of T2DM we do not anticipate that these assumptions will have a big influence on the results as the cardiovascular disease and cancer outcomes that are linked to overweight status in the model do not occur until old age, which for children will not occur for many decades when the model results will be heavily discounted.

Fourth, we will explicitly model lag times between changes in soft drink consumption and health outcomes, with reference to models that have explored time lag between dietary change and health.⁶⁶ The assumptions around time lag will be tested in sensitivity analyses. Fifth, we will re-parameterise the model for the whole UK (currently the model is parameterised for England) using data on health statistics from the Office for National Statistics, the General Register Office for Scotland, the Northern Ireland Statistics and Research Agency and UK results from the Global Burden of Disease study.

Study populations & data sources

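### WP2 drives modelled dental caries by drink sugar alone, although its caries relation is on sugar consumption and WP1 measures confectionery and all-source sugar

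*Protocol*

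**What the plan says.** **What WP1 measures (section 7.1).** Study 1b includes confectionery as one other high-sugar category and gives the reason: "Identifying decreases in purchases of levy-eligible drinks alongside increases in confectionery would alert us to possible unintended consequences of the intervention". Its outcomes include "mean 4-weekly total sugars (in kg and £) in confectionery purchased per household". Study 1c, on the national diet survey, adds "mean daily added sugars (g) consumed in confectionery and from all sources".

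**What WP2 takes from WP1 (section 7.2).** Under Study design, the WP1 results "will be used to estimate effect sizes in terms of sugary drink consumption and free sugars from drinks". Under Proposed methods, soft drink volume and soft drink sugar concentration are converted to an equivalised sugar drink intake. The first development of the model then repeats the restriction: "Here, the inputs will be changes in consumption of sugar drinks (from the interrupted time series analysis of the Kantar World Panel dataset"), plus the change in sugar level of those drinks from FoodDB. Under Proposed outcome measures, caries is listed with obesity and type 2 diabetes as changing because of soft drink consumption and soft drink sugar level.

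**How caries is modelled.** "For dental caries we will model the impact between sugar consumption and disease outcome using results from a prospective cohort study". This sentence does not limit the sugar to drinks.

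**Where the result goes (section 7.3).** Both economic analyses take their health impact from the WP2 model. Confectionery enters WP3 as price, demand and substitution data.

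**The concern.** For caries, the exposure on which the relation is defined and the exposure change fed into it are not the same quantity. The relation is on sugar consumption; the supplied change is sugar from drinks. The two agree only if sugar from everything else is unaffected by the levy, which is the assumption that the confectionery outcome was included to test.

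The study could therefore report in WP1 that confectionery sugar moved, while the caries cases, caries-related QALYs and caries treatment costs from WP2 and WP3 were computed as though it had not. Section 7.1 (Outcome measures) describes the levy's primary aim as lowering sugar intake rather than soft drink intake, so the net quantity is the one of interest.

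**Working it through.** The plan states no figure on this point, so there is none to reproduce. The check traces inputs and then scales the effect.

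**1. Trace of each sugar outcome into the caries model**

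| WP1 outcome | Source | Used as health exposure in WP2? |
|---|---|---|
| Sugar drink volume | Household panel, Study 1b | Yes |
| Drink sugar concentration | FoodDB, Study 1a | Yes |
| Confectionery sugar | Household panel, Study 1b | No |
| Added sugar, all sources | Diet survey, Study 1c | No |

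**2. Could another planned step carry it in?**
- The sensitivity analyses named in section 7.2 cover tracking of childhood overweight, time lag, early implementation stages and discounting. None covers substitution.
- The Monte Carlo intervals and tornado plots vary parameters that are in the model. They cannot show a pathway that is left out.
- The comparison with hospital admissions and child measurement data is a short-term validity check, made where possible. It does not alter the inputs.
- WP3 uses confectionery on the spending side and takes health effects from WP2.
- WP5 synthesises findings but prescribes no re-run of the model.

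**3. Size for an assumed offset**

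Let D be the drink sugar removed (g/day) and sD the accompanying rise in confectionery sugar; a negative s is a fall. Then:
- modelled change = D
- change in drinks plus confectionery = D(1 - s)
- ratio = D / [D(1 - s)] = 1/(1 - s)

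| Assumed s | Ratio of modelled to actual change |
|---|---|
| 40% | 1/0.60 = 1.67 |
| 20% | 1/0.80 = 1.25 |
| 10% | 1/0.90 = 1.11 |
| 0 | 1.00 |
| -10% | 1/1.10 = 0.91 |
| -20% | 1/1.20 = 0.83 |

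**4. Illustration in grams.** Section 7.1, Study 1d uses 50 ml/day as the trigger for the child adiposity analysis. It is not an expected effect and serves here only as a convenient scale. At an assumed 10 g/100 ml, 50 × 10/100 = 5 g/day is removed.
- Confectionery up 1 g/day: 5 - 1 = 4 g/day net, ratio 5/4 = 1.25.
- Confectionery up 2 g/day: 5 - 2 = 3 g/day net, ratio 5/3 = 1.67.
- Confectionery down 1 g/day: 5 + 1 = 6 g/day net, ratio 5/6 = 0.83.

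At an assumed 5 or 8 g/100 ml the sugar removed is 2.5 or 4.0 g/day, and a 1 g/day rise gives 2.5/1.5 = 1.67 or 4.0/3.0 = 1.33.

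These ratios apply to sugar exposure. They carry over to caries only if the relation is close to linear over so small a change.

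**The case against.** **The caries sentence could mean all-source sugar.** Read alone, it could. But the Study design, the list of inputs and the Proposed outcome measures in section 7.2 all name drinks only, and the last of these names caries. At the least the text is unclear on which exposure is meant.

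**Nothing forbids a net-sugar scenario.** True: section 7.3 allows scenarios informed by WP4 and mentions analysing substitution towards confectionery, and WP5 brings the findings together. So it would be too strong to say that substitution can never reach the modelled results. No step requires it, however.

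**A reader might infer that the bias always favours the levy.** The documents do not support that. Appendix B lists substitution, complementing and other responses for purchases of other products. Section 4.1 says that media coverage may stress the health risks of sugary drinks, which might also lower other sugar intake. The error can run either way.

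**A reader might infer that modelled obesity, diabetes and headline QALYs are overstated too.** This does not follow. Section 7.2 models body weight from effects of sugar drinks on weight, and type 2 diabetes directly from soft drinks. Such drink-specific effects may already contain some dietary compensation, so subtracting confectionery sugar gram for gram could count it twice. The protocol also does not say how much of the total QALY or cost result comes from caries.

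**The expectation in section 7.3 that the levy will be dominant might look like prejudged benefit.** The reason given there is that implementation costs fall outside the NHS, which is unrelated to substitution.

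**Conclusion.** The point holds for dental caries. As written, WP2 supplies a drinks-only exposure change to a relation on sugar consumption, leaves out two sugar outcomes that WP1 already plans, and names no sensitivity analysis to cover the gap. The consequence is conditional: if confectionery sugar does not respond to the levy, the omission of confectionery causes no error. If it rises, modelled caries benefit and its share of WP3 QALYs and costs are too favourable; if it falls, they are too unfavourable.

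The size cannot be derived from the documents. The factor 1/(1 - s) rests entirely on assumed s, and the gram example also on an assumed sugar concentration. It shows that moderate offsets would matter, not that they are expected. A material error in the overall QALY or cost results is not shown.

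**What to change.** In section 7.2, Proposed methods:

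1. State which sugar exposure the caries relation uses.
2. Run the caries model with three exposure changes and report them side by side: drinks only; drinks plus confectionery from Study 1b; and added sugar from all sources from Study 1c. Carry the uncertainty of each estimate into the Monte Carlo.
3. Label the second run drinks plus confectionery, not total net sugar. Section 7.1 says that confectionery is the one food category bought from the panel for reasons of cost, so other substitutes are not captured.
4. Carry all three results into the caries costs and QALYs in WP3.
5. For weight-mediated diseases and type 2 diabetes, keep the drink-specific effects as the main analysis. A confectionery offset there should be an optional sensitivity scenario, with the risk of double-counting compensation stated.

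**Cost.** One or two extra model runs on outcomes already planned, with no new data. Study 1b sugar is total sugar per household and Study 1c is added sugar per person, so the conversions must be written down; the drink volumes are per household and need the same step. Intervals will widen, most with the diet survey, which has about 2,000 people after implementation against 30,000 panel households per time point.

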7.4 WP4 – Impacts on key stakeholders: the public, politicians and professionals

Study design

We will collect data to develop an understanding of the impacts of the SDIL and responses to it from key stakeholder groups including the public, industry, media and government. Quantitative and qualitative methods will be employed as follows:

- Thematic analysis will be undertaken to identify predominant discourses relating to sugar and the SDIL using documentary sources including: media coverage, political discourse & industry communications
- Analysis of social media (Twitter) to identify predominant discourses relating to sugar and the SDIL, and the spread of discourses over time and between groups.
- Longitudinal qualitative research comprising one-to-one interviews and focus groups will be used to gauge the reactions of the public and key stakeholder groups to the SDIL

Study populations, sampling and recruitment

Study populations for the qualitative components will be sampled as follows:

Food industry reactions to the SDIL will be tracked in two ways:

- *Food industry trade press*, such as The Grocer magazine. The range of relevant trade press media will be identified by iterative searching of the internet and the LexisNexis database. A sampling strategy will be determined, dependent on the volume of material and frequency of publication, aiming to achieve thematic saturation to ensure that changes in discourse can be tracked over time across the implementation phases of the SDIL.
- *In depth telephone interviews* with a purposive sample of professionals representing key sectors of the food industry with interests in SSBs, which will include manufacturers, distributors, retailers, and vendors. Participants will be identified through snowball sampling, starting with the extensive database of contacts we have developed in our formative work (stakeholder consultation on the SDIL systems map). Informed consent will be obtained verbally and documented by the researcher. Interviews in each implementation phase will continue until saturation has been achieved, building on interviews conducted as part of our formative research (current NIHR PHR Rapid Funding Grant). A maximum of 15 interviews per phase will be undertaken. Where they are willing, interviewees will be asked to participate in interviews across each phase of the SDIL evolution and implementation, so as to gain a longitudinal view of discourses on sugar consumption and the SDIL.

Public discourse surrounding the SDIL will be similarly tracked in three ways:

- *News media coverage* will be identified by interrogating the LexisNexis database using a pre-determined search strategy that will be refined following initial scoping, to identify all articles referring to regulation of sugar in food/drinks, or to the SDIL specifically in national newspapers and trade (food industry) press from 2 years before announcement of the levy until 2 years after implementation. It is likely that articles will be clustered sporadically. Searches and screening of articles will therefore take place at the end of time periods 2-3. Depending on the volume of material, we may need to sample articles from each time period to limit workload, while achieving thematic saturation. The majority of national press articles can be accessed online, where public reactions to articles can also be found. This public discourse will also be sampled and analysed iteratively, to saturation.
- *Social media discourse* will be identified via analysis of Tweets, which will be collected using both specific keywords and also by following Twitter accounts of key individuals and bodies, from October 2016 until March 2020. This will include data on public and professional (e.g. public health, industry) discourse, as well as advocacy from civil society organisations and individuals, which will be triangulated with other sources (see below). Relevant tweets from each of the four time periods will be identified using search strategies (determined during our current formative work) to identify discourse on the SDIL. Key sources (twitter accounts) identified as commenting on the SDIL in early searches will be routinely searched in subsequent searches for continuing discourse (e.g. Faculty of Public Health, British Soft Drinks Association, Jamie Oliver). The volume of material is likely to be high. For qualitative analysis, to ensure a manageable quantity of data, we will prioritise 'popular' tweets (e.g. highly retweeted) and those from key stakeholders, as well as sample material for content analysis, which will continue to saturation. We will also undertake network analysis to explore the spread of discourses between groups and over time. Detailed methods are being developed in our formative work.

- *Focus groups with members of the public*, including parents, secondary school children and young adults (16-24 years), will be undertaken to identify degree of consensus on the potential acceptability and impacts of the SDIL. Purposive sampling will aim to achieve maximum variation with regard to geography (UK countries/regions), age (12-15, 16-24, 25-44, 45-74 years), gender (male, female) and socio-economic position (non-manual occupations, manual occupations). We will work with NIHR's People in Research (www.peopleinresearch.co.uk) to recruit adults for focus groups. Secondary school pupils will be identified via their parents and approached with parental consent. We will recruit 10-12 participants per focus group. We will aim to achieve focus groups that are relatively homogeneous within each group, but diverse across groups, with a view to identifying in particular the degree of consensus on issues of interest. A sub-sample of volunteers who agree to take part in multiple focus groups across the phases of SDIL evolution and implementation, will join groups that will act as panels, to gain a longitudinal view of discourses on sugar consumption and the SDIL. We will sample and analyse focus group discussions iteratively, aiming to achieve saturation. We anticipate conducting approximately 5 focus groups in each of time periods 2-4, a total of 15 groups.

Political discourse on the SDIL will be identified from Hansard (official record of Parliamentary sessions), select committee records and published records (e.g. policy documents) of key departments (e.g. HM Treasury, Department of Health). A key analysis will focus on the material submitted to the HM Treasury consultation on the SDIL during summer 2016, when this is made publicly available. We anticipate analysing this data in its entirety, but if the volume is too great, we will determine a sampling strategy to ensure a representative range of views are contained in the data.

Political advocacy arising from public health and other groups (e.g. UK Health Forum, Sustain and Children's Food Campaign), including groups opposed to the SDIL (e.g. Institute of Economic Affairs (IEA), Food and Drink Federation (FDF)) will be tracked by identifying and monitoring relevant media over the course of the study (which may include social media, web sites, press releases and newsletters). These media will first be identified through internet and social media searches and our searches of LexisNexis (see above), and then sampled if necessary to ensure a representative but manageable volume of material is analysed to achieve saturation.

Data collection

- Document analysis: Documents to be analysed will be retrieved electronically where feasible (e.g. from online sources) and saved as digital files. Documents only available in hard copy will be scanned to create digital files. Complete texts will be extracted and entered into NVivo/Atlas.ti for analysis.
- Twitter analysis: Automated methods to harvest relevant tweets using pre-specified search strategies are being developed in our formative work.
- Interviews and focus groups: data collection will be supported by topic guides that will be informed by existing theory and discourses, and developed with stakeholder input (professional or public as appropriate) and piloted prior to formal data collection. Topic guides for interviews and focus groups will ask about participants' perceptions of the potential benefits and harms of the SDIL to any individuals or sectors, as well as attitudes to fiscal food policies and the SDIL in particular. Interviews and focus groups will be digitally recorded with participants' permission and transcribed verbatim. Transcripts will be checked by the interviewer and then entered into NVivo/Atlas.ti for analysis. Interviewers' notes will be transcribed verbatim and entered into NVivo/Atlas.ti for analysis alongside transcripts.

Data analysis

- Documentary sources, including news and social media content: Data from documentary sources will be analysed qualitatively using thematic content or critical discourse analysis, as appropriate, assisted by NVivo software. Rather than a static analysis at a single point in time, sequential analyses will be undertaken using data from key time segments corresponding to the phases of the introduction of the SDIL (i.e. mirroring the quantitative analyses). Using this approach we will be able to explore how prevailing narratives for each group of interest (public, professional, industry, political) develop over time as plans for the SDIL develop and solidify. A dialogue between the qualitative and quantitative analyses will allow us to explore the extent to which the development of narratives appear to be contingent on the emerging processes and outcomes of the SDIL. This approach will be strengthened by longitudinal analysis of data from key sources with ongoing⁸⁰ discourse on the SDIL (e.g. specific newspapers, trade journals or twitter accounts). We will also use network⁸¹ and sentiment analysis⁸² of the accumulated relevant tweets to identify the trends, spread and emergence of discourses, and relationships between key stakeholder discourses.
- Interview and focus group data: Data from face to face dialogues will be analysed thematically,⁸⁰ assisted by NVivo/Atlas.ti software, using the Framework method⁸³ with constant comparison⁸⁴ and deviant case analysis⁸⁵ to enhance validity. Initial frameworks will be developed from interview topic guides and modified iteratively using emergent themes, so that earlier transcripts influence the analysis of subsequent transcripts. As with the analysis of documents, interviews and focus groups will be analysed in time segments corresponding to the implementation phases of the SDIL. The enquiry will be strengthened by longitudinal analysis of data from focus group panels allowing investigation of emerging discourse on the SDIL.

All data will be anonymised following transcription to preserve the anonymity of individual participants or organisations where possible. A sample of all qualitative data will be independently analysed by a second researcher to ensure reliability of the thematic coding frameworks. Data clinics involving WP4 team members will also be held to achieve consensus in data interpretation. Any data that are unavoidably identifiable will only be used with the consent of the relevant participants.

